6.4 Exclusion Criteria

Each subject must not:

1. Have any clinically significant slit-lamp findings at Visit 1, including active blepharitis; meibomian gland dysfunction (MGD); lid margin inflammation; or active ocular allergies that require therapeutic treatment, or, in the opinion of the investigator may interfere with the assessment of the safety or efficacy of reproxalap or vehicle;
2. Have or be diagnosed with an ongoing ocular infection (bacterial, viral, or fungal) or active ocular inflammation at Visit 1;
3. Have worn contact lenses within 7 days of Visit 1 or anticipate using contact lenses during the study;
4. Have used any eye drops within 2 hours of Visit 1;
5. Have previously had laser-assisted in situ keratomileusis (LASIK) surgery within the last 12 months;
6. Have used ophthalmic cyclosporine or lifitigrast 5.0% ophthalmic solution within 90 days of Visit 1;
7. Have any planned ocular and/or lid surgeries over the study period or any ocular surgery within 6 months of Visit 1;
8. Have used temporary or permanent punctal plugs within 30 days prior to Visit 1 or anticipate their use during the study period;

9. Be currently taking any topical ophthalmic prescription (including medications for glaucoma) or over-the-counter (OTC) solutions, artificial tears, gels or scrubs, that cannot be discontinued for the duration of the trial (excluding medications allowed for the conduct of the study);
10. Have corrected visual acuity (VA) [REDACTED]
[REDACTED]
[REDACTED]
11. Be a woman who is pregnant, nursing, or planning a pregnancy during the trial;
12. Be unwilling to submit a urine pregnancy test at Visit 1 and Visit 9 (or early termination visit) if of childbearing potential. Non-childbearing potential is defined as a woman who is permanently sterilized (e.g., has had a hysterectomy or tubal ligation), or is post-menopausal (without menses for 12 consecutive months);
13. Be a man or woman of childbearing potential who is not using an acceptable means of birth control; acceptable methods of contraception include: hormonal – oral, implantable, injectable, or transdermal contraceptives; mechanical – spermicide in conjunction with a barrier such as a diaphragm or condom; intrauterine device (IUD); or surgical sterilization of males or partner. For non-sexually active males or females, abstinence may be regarded as an adequate method of birth control; however, if the subject becomes sexually active during the study, he/she must agree to use adequate birth control as defined above for the remainder of the study;
14. Have a known allergy and/or sensitivity to reproxalap or the test article excipients;
15. Have a condition or be in a situation which the investigator feels may put the subject at significant risk, may confound the study results, or may interfere significantly with the subject's participation in the study;
16. Be currently enrolled in an investigational drug or device study or have used an investigational drug or device within 30 days of Visit 1;
17. Have previously participated in a reproxalap ophthalmic solution study;
18. Be currently using any medication known to cause ocular drying that has not been used on a stable dosing regimen for at least 30 days prior to Visit 1;
19. Be unable or unwilling to follow instructions, including participation in all study assessments and visits.

6.5 **Withdrawal Criteria (if applicable)**

If at any time during the study the investigator determines that a subject's safety has been compromised, the subject may be withdrawn from the study.

Subjects may withdraw consent from the study at any time.

The Sponsor and investigators may discontinue any subject for non-compliance, or for any medical reason.

7 STUDY PARAMETERS

7.1 Efficacy Measures and Endpoints

7.1.1 Primary Efficacy Measure(s)

- Subject-reported ocular dryness

7.1.2 Primary Efficacy Endpoint

- The primary endpoint is the overall mean change from baseline in subject-reported ocular dryness score [REDACTED] assessed using MMRM from Week 2 to Week 12. The population used for analysis of ocular dryness score will be subjects who have a baseline ocular dryness score [REDACTED]

7.1.3

7.1.8 Criteria for Effectiveness

The primary endpoint will be achieved if the overall mean change from baseline in subject-reported ocular dryness score [REDACTED] assessed [REDACTED] [REDACTED] from Week 2 to Week 12, in reproxalap-treated subjects is statistically significantly lower than that of vehicle-treated subjects. The population used for analysis of ocular dryness score will be subjects who have a baseline (Visit 2) ocular dryness score of [REDACTED]

7.2 Safety Measures

- Visual acuity at distance utilizing an ETDRS chart
- Slit-lamp evaluation
- Adverse event query (reported, elicited and observed)
- IOP
- Dilated fundoscopy

8 STUDY MATERIALS

8.1 Study Treatment(s)

8.1.1 Study Treatment(s)/ Formulation(s):

- Reproxalap Ophthalmic Solution (0.25% Novel Formulation)
- Vehicle Ophthalmic Solution (vehicle)

8.1.2 Description of and Justification for the Route of Administration, Dosage, Dosage Regimen, and Treatment Period(s):

Topical ophthalmic dosing is the optimal route of administration for DED treatment. The dosage and dosage regimen were selected based on nonclinical and clinical studies described in Section 2. The proposed treatment period of 12 weeks is based on the Phase 2 clinical trials and on the anti-inflammatory mechanism of action of reproxalap.

8.1.3 Instructions for Use and Administration

- Reproxalap and vehicle are supplied as patient kits, with each kit containing 15 foil pouches, and each foil pouch containing five single-dose units.
- The vehicle solution consists of all components of the drug product solution with the exception of reproxalap.
- At the study site, all Investigational Product (IP) must be stored under the conditions specified in the Investigator's Brochure in a secure area accessible only to the designated qualified clinical site personnel. All IP must be stored, inventoried and the inventories carefully and accurately documented according to applicable state, federal and local regulations, International Council on Harmonisation (ICH) Good Clinical Practices (GCPs) and study procedures.
- Reproxalap and vehicle should be stored refrigerated (2–8° C). Subjects will be instructed to store reproxalap and vehicle in a refrigerator (2–8° C). Five cavity unit dose ampules are packaged in aluminum foil pouches under nitrogen. Unit dose ampules are for SINGLE USE ONLY.
- Subjects will receive four treatment kits. After Visit 5 all subjects will change their dosing regimen from QID to BID for the remainder of the treatment period.
- At a minimum, the immediate or secondary study drug packaging will provide the following information: study Sponsor identification, directions for use, required storage conditions, caution statements (including “New Drug–Limited by Federal Law to Investigational Use” language), and study identification.

8.2 **Other Study Supplies**

Other study supplies include urine pregnancy tests, Schirmer's test strips, sodium fluorescein, lissamine green, Fluress, Tropicamide, VAS rulers, and Tear Osmolarity cards.

9 STUDY METHODS AND PROCEDURES

9.1 **Subject Entry Procedures**

9.1.1 Overview

Subjects as defined by the criteria in sections 6.3, 6.4, and 6.5 will be considered for entry into this study.

9.1.2 Informed Consent

Prior to a subject's participation in the trial (i.e., changes in a subject's medical treatment and/or study related procedures), the study will be discussed with each subject, and subjects wishing to participate must give written informed consent (and/or assent) using an informed consent form. The informed consent form must be the most recent version

that has received approval/favorable review by a properly constituted Institutional Review Board (IRB)/Independent Ethics Committee (IEC).

9.1.3 Washout Intervals

Prohibited medications, treatments, and activities are outlined in the exclusion criteria (Section 6.4).

9.1.4 Procedures for Final Study Entry

Subjects must meet all inclusion and none of the exclusion criteria.

9.1.5 Methods for Assignment to Treatment Groups:

Before the initiation of study run-in at Visit 1, each subject who provides written and informed consent will be assigned to a screening number. All screening numbers will be assigned in strict numerical sequence at a site and no numbers will be skipped or omitted. Each subject who meets all the inclusion and none of the exclusion criteria at Visit 1 and Visit 2 will be assigned a randomization number at the end of Visit 2. The Interactive Web Response System (IWRS) will be used to assign all randomization numbers.

Subjects are to be stratified by Visit 2 (Baseline) [REDACTED] and Visit 2 (Baseline) Pre-CAE fluorescein nasal staining score in the study (worst) eye using the following strata:

- [REDACTED]
- [REDACTED]
- [REDACTED]
- [REDACTED]

[REDACTED] will continue until the sample size for the co-primary analysis described in Section 11.3 has been achieved.

Randomization and kit numbers will be assigned automatically to each subject as they are entered into the IWRS.

The site staff will dispense kit(s) required until the next visit. Both the randomization number and the dispensed study drug kit number(s) will be recorded on the subject's source document and electronic case report form (eCRF). The Sponsor, investigators, and study staff will be masked during the randomization process and throughout the study.

9.2 Concurrent Therapies

The use of any concurrent medication, prescription or over-the-counter, is to be recorded on the subject's source document and corresponding case report form (CRF) along with the reason the medication was taken.

Concurrent enrollment in another investigational drug or medical device study is not permitted.

9.2.1 Prohibited Medications/Treatments

Disallowed medications/treatments during the study are outlined in the Exclusion Criteria (Section 6.4).

9.2.2 Escape Medications

No escape medications are required for this study.

9.2.3 Special Diet or Activities

No special diets or activities are required for this study.

9.3 Examination Procedures

9.3.1 Procedures to be Performed at Each Study Visit with Regard to Study Objective(s)

Procedures listed below should be performed in the given order. See Appendix 2 on methodologies and grading systems.

9.3.2 Visit 1: Day -14 ± 2 – [REDACTED]

All subjects will undergo the following screening assessments:

[REDACTED]
[REDACTED] Consent/HIPAA

- Demographic Data and Medical/Medication/Ocular History
- Review of Inclusion/Exclusion Criteria
- Urine Pregnancy Test (for females of childbearing potential): Women of childbearing potential must have a negative urine pregnancy test to continue in the study
- Multi-symptom Visual Analogue Scale (VAS)
- [REDACTED]
- [REDACTED]
- [REDACTED]
- [REDACTED]
- BCVA Utilizing an ETDRS Chart
- Slit Lamp Biomicroscopy
- [REDACTED]
- Fluorescein Staining (corneal and conjunctival)
- Lissamine Green Staining (corneal and conjunctival)

[figure not shown]
[REDACTED]

- [REDACTED]
- [REDACTED]
- [REDACTED]
- Slit Lamp Biomicroscopy
- [REDACTED]
- IOP
- Dilated Fundoscopy
- Review of Inclusion/Exclusion Criteria
- Run-in Instillation at the Study Site: All subjects having a positive response (as defined above) and meeting all other screening eligibility criteria at the end of Visit 1 will receive run-in drops for dosing. Qualified subjects will self-administer their initial run-in dose bilaterally at the study site under the supervision of a trained technician.
- Run-in Dispensation: Prior to discharge from the study site on Day -14, subjects will be dispensed sufficient Run-in supply to last until Visit 2 and will be educated on self-administration of vehicle run-in. Subjects will be instructed to self-administer one drop QID in each eye until Visit 2. Subjects will be instructed NOT to instill run-in on the morning of their next scheduled study visit (Visit 2).
- AE Query
- Subjects will be scheduled for Visit 2.

[figure not shown]
9.3.3 Visit 2: Day 1 – [REDACTED] Confirmation and Baseline

- [REDACTED]
- Study Run-in Collection
- Review of Inclusion/Exclusion Criteria
- Medical/medication history update
- AE query
- Multi-symptom Visual Analogue Scale (VAS)
- [REDACTED]

- [REDACTED]
- [REDACTED]
- [REDACTED]
- BCVA Utilizing an ETDRS Chart
- Slit Lamp Biomicroscopy

- At least 15-minute wait between lissamine green staining and Schirmer's test
- [REDACTED]
- [REDACTED]
- [REDACTED] every 5 minutes thereafter;

- Slit Lamp Biomicroscopy
- Review of Inclusion/Exclusion Criteria
- Randomization
- Study Drug Instillation at the Study Site: All subjects having a positive response (as defined above) and meeting all other screening eligibility criteria at the end of Visit 2 will be randomized to one of two treatment groups utilizing the IWRS system. Randomized subjects will self-administer their initial study drug dose bilaterally at the study site under supervision of a trained technician. Subjects will be instructed to dose four times a day (QID) in both eyes until their next visit.
- Study Drug Dispensation: Prior to discharge from the study site on Visit 2 (Day 1), randomized subjects will be educated on self-administration of study drug. Subjects

will receive their assigned study drug kit with sufficient supply to last until Visit 3 and will be instructed NOT to self-administer study drug on the morning of their next scheduled study visit (Visit 3).

- AE Query
- Subjects will be scheduled for Visit 3.

9.3.4 Visit 3 (Day 8 ± 2)

- Study Drug Collection
- Medical/medication history update
- AE query
- Multi-symptom Visual Analogue Scale (VAS)
- [REDACTED]
- [REDACTED]
- [REDACTED]
- [REDACTED]
- [REDACTED]
- BCVA Utilizing an ETDRS Chart
- Slit Lamp Biomicroscopy
- [REDACTED]
- [REDACTED]
- [REDACTED]
- Study Drug Dispensation: Prior to discharge from the study site on Visit 3, subjects will be re-dispensed the remaining unused ampules from their previous kit for at-home dosing up to Visit 4. Subjects will be reinstructed to dose four times a day (QID) in both eyes until their next visit.
- Subjects will again be educated on self-administration of study drug. Subjects will be instructed to NOT self-administer study drug on the morning of their next scheduled study visit (Visit 4)
- AE Query
- Subjects will be scheduled for Visit 4.

9.3.5 Visit 4 (Day 15 ± 2)

- Study Drug Collection

- Medical/medication history update
- AE query
- Multi-symptom Visual Analogue Scale (VAS)
- [REDACTED]
- [REDACTED]
- [REDACTED]
- [REDACTED]
- BCVA Utilizing an ETDRS Chart
- Slit Lamp Biomicroscopy

[figure not shown]

- Study Drug Dispensation: Prior to discharge from the study site on Visit 4, subjects will be assigned a new study drug kit via the IWRS and will also be re-dispensed the remaining unused ampules from their previous kit for at-home dosing up to Visit 5. Subjects will be reinstructed to dose four times a day (QID) in both eyes until their next visit.
- Subjects will again be educated on self-administration of study drug. Subjects will be instructed to NOT self-administer study drug on the morning of their next scheduled study visit (Visit 5)
- AE Query
- Subjects will be scheduled for Visit 5.

9.3.6 Visit 5 (Day 29 ± 2)

- Study Drug Collection
- Medical/medication history update
- AE query
- Multi-symptom Visual Analogue Scale (VAS)
- [REDACTED]
- [REDACTED]
- [REDACTED]

- [REDACTED]
- [REDACTED]
- BCVA Utilizing an ETDRS Chart
- Slit Lamp Biomicroscopy

[figure not shown]

- Study Drug Dispensation: Prior to discharge from the study site on Visit 5, subjects will be assigned a new study drug kit via the IWRS and will also be re-dispensed the remaining unused ampules from their previous kit for at-home dosing up to Visit 6.
- Subjects will now switch to the BID treatment regimen. Subjects will be instructed to dose twice a day (BID) in each eye through the end of the treatment period.
- Subjects will again be educated on self-administration of study drug. Subjects will be instructed to NOT self-administer study drug on the morning of their next scheduled study visit (Visit 6)
- AE Query
- Subjects will be scheduled for Visit 6.

9.3.7 Visit 6 (Day 43 ± 2)

- Study Drug Collection
- Medical/medication history update
- AE query
- Multi-symptom Visual Analogue Scale (VAS)
- [REDACTED]
- [REDACTED]
- [REDACTED]
- [REDACTED]
- BCVA Utilizing an ETDRS Chart

- Slit Lamp Biomicroscopy

- Study Drug Dispensation: Prior to discharge from the study site on Visit 6, subjects will be re-dispensed the remaining unused ampules from their previous kits for at-home dosing up to Visit 7. Subjects will be reinstructed to dose BID in both eyes until their next visit.
- Subjects will again be educated on self-administration of study drug. Subjects will be instructed to NOT self-administer study drug on the morning of their next scheduled study visit (Visit 7)
- AE Query
- Subjects will be scheduled for Visit 7.

9.3.8 Visit 7 (Day 57 ± 3)

- Study Drug Collection
- Medical/medication history update
- AE query
- Multi-symptom Visual Analogue Scale (VAS)
- [REDACTED]
- [REDACTED]
- [REDACTED]
- [REDACTED]
- BCVA Utilizing an ETDRS Chart
- Slit Lamp Biomicroscopy

[figure not shown]

- Study Drug Dispensation: Prior to discharge from the study site on Visit 7, subjects will be assigned a new study drug kit via the IWRS and will also be re-dispensed the remaining unused ampules from their previous kit for at-home dosing up to Visit 8. Subjects will be reinstructed to dose BID both eyes until their next visit.

- Subjects will again be educated on self-administration of study drug. Subjects will be instructed to NOT self-administer study drug on the morning of their next scheduled study visit (Visit 8)
- AE Query
- Subjects will be scheduled for Visit 8.

9.3.9 Visit 8 (Day 71 ± 3)

- Study Drug Collection
- Medical/medication history update
- AE query
- Multi-symptom Visual Analogue Scale (VAS)
- [REDACTED]
- [REDACTED]
- [REDACTED]
- [REDACTED]
- [REDACTED]
- BCVA Utilizing an ETDRS Chart
- Slit Lamp Biomicroscopy

[figure not shown]

- Study Drug Dispensation: Prior to discharge from the study site on Visit 8, subjects will be re-dispensed the remaining unused ampules from their previous kit for at-home dosing up to Visit 9. Subjects will be re-instructed to dose BID in both eyes until their next visit.
- Subjects will again be educated on self-administration of study drug. Subjects will be instructed to NOT self-administer study drug on the morning of their next scheduled study visit (Visit 9)
- AE Query
- Subjects will be scheduled for Visit 9.

9.3.10 Visit 9 (Day 85 ± 3)

- Study Drug Collection

- Medical/medication history update
- AE query
- Urine Pregnancy Test (for females of childbearing potential): Women of childbearing potential must have a negative urine pregnancy test to continue in the study
- Multi-symptom Visual Analogue Scale (VAS)
- [REDACTED]
- [REDACTED]
- [REDACTED]
- [REDACTED]
- BCVA Utilizing an ETDRS Chart
- Slit Lamp Biomicroscopy

- IOP
- Dilated Fundoscopy
- AE Query
- Study Exit

9.3.11 Early Termination/Discontinuation

If a subject is discontinued from the study prior to Visit 9 (Day 85 ± 3), then all safety evaluations that are to be performed at Visit 9 should be performed on the day of discontinuation (early termination) or at the discretion of the investigator.

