In 1995, Augustin et al. ([Augustin 1995](#)) described elevations in tear MDA levels that correlated with severity in DED patients. Subsequently, Choi et al. ([Choi 2016](#)) reported that expression of MDA and 4-hydroxynonenal (another RASP commonly associated with inflammation) is increased in the tear film and ocular surface of patients with DED. Consistent with the literature that supports the notion that RASP mediate pro-inflammatory toxicity in DED, the anti-inflammatory effects of the RASP scavenger reproxalap have been demonstrated in Phase 2 clinical trials in DED, noninfectious anterior uveitis, and allergic conjunctivitis. In aggregate, a broad array of preclinical and clinical evidence supports the use of reproxalap for the treatment of ocular inflammation, including DED.

2 Clinical Studies of Reproxalap Ophthalmic Solution

Reproxalap ophthalmic solution is in clinical development for the treatment of ocular inflammation. The drug product, in various strengths, has completed a Phase 1 clinical trial, as well as a vehicle-controlled, double-masked Phase 2a clinical trial in allergic conjunctivitis; a vehicle-controlled, double-masked Phase 2b clinical trial in allergic conjunctivitis; a comparator-controlled, investigator-masked Phase 2 clinical trial in noninfectious anterior uveitis; a vehicle-controlled, double-masked Phase 2a clinical trial in DED; and a vehicle-controlled, double-masked Phase 2b clinical trial in DED. Phase 3 clinical trials in noninfectious anterior uveitis and allergic conjunctivitis are in progress. A total of 468 subjects have been exposed to topical ocular reproxalap in completed clinical trials.

In all clinical trials, no treatment-related serious adverse events (SAE) have been observed. Generally mild to moderate transient ocular stinging, lasting only up to a few minutes, was reported in most subjects treated in the Phase 1 and the allergic conjunctivitis and dry eye disease Phase 2 clinical trials, and in a small proportion of

subjects in the noninfectious anterior uveitis Phase 2 and the allergic conjunctivitis Phase 2b clinical trials. Table 1 summarizes the clinical exposure to topical ocular reproxalap for completed clinical trials.

Allogene Therapeutics, Inc.
Final V2 017Dec2019

Final V2.0 17Dec2019

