5 OVERALL STUDY DESIGN

The clinical trial is a Phase 2, multicenter, randomized, double-masked, parallel-group, vehicle-controlled design with block enrollment. Subjects will be randomized to one of the following treatment groups at Visit 2 and will be instructed to follow a dosing regimen QID dosing for four weeks followed by BID dosing for weeks 5-12:

- Reproxalap Ophthalmic Solution (0.25% Novel Formulation)
- Vehicle Ophthalmic Solution (vehicle)

[figure not shown]
Approximately 200 subjects will be randomly assigned to one of the two treatment groups (1:1) to receive either Reproxalap Ophthalmic Solution (0.25% Novel Formulation) or vehicle solution as topical ophthalmic drops administered bilaterally QID for four weeks followed by BID dosing for weeks 5-12. Subjects, Sponsor, CRO and site personnel will be masked to treatment assignment.

[figure not shown]
During the screening period, two 90-minute exposures to the CAE® will be conducted to ascertain eligibility to enter the study. Those who qualify will be randomized to receive study drug in a double-masked fashion for 84 days. Subjects will self-administer drops daily as instructed.

At Visits 3 - 9, no CAE® exposure will occur but signs and symptoms will be assessed.

All subjects will dose with randomized treatment QID between Visit 2 and Visit 5 and switch to BID dosing between Visit 5 and Visit 9.

The total number of expected participants, including screen failures, is approximately 500 subjects.

Subjects who terminate early during the treatment period will be asked to complete safety assessments prior to commencement of alternative DED therapy (if possible). Subjects who are terminated early from the study will not be replaced.

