10.4 Procedures for Unmasking (if applicable)

All subjects, investigators, and study personnel involved with the conduct of the study will be masked with regard to study drug treatment assignments. When medically necessary, the investigator may need to determine what treatment has been assigned to a subject. When possible (i.e., in non-emergent situations), Ora and/or the Sponsor should be notified before unmasking IP. Ora and/or the study Sponsor must be informed immediately about any unmasking event.

If an investigator identifies a medical need for unmasking the treatment assignment of a subject, he/she should contact Ora and/or the medical monitor prior to unmasking the identity of the IP, if possible. Ora will ask the site to complete and send them the Unmasking Request Form. Ora will notify Aldeyra and jointly will determine if the unmasking request should be granted. They may consult the medical monitor as needed. The result of the request will be documented on the Unmasking Request Form. If approval is granted to unmask a subject, written permission via the Unmasking Request Form will be provided to the investigator. The investigator will unmask the subject using IWRS. The investigator will complete the Unmasking Memo form and include it in the subject's study file and provide a copy for the TMF. For each unmasked request, the reason, date, signature, and name of the person who unmasked the subject, must be noted in the subject's study file.

Unmasked subjects will be discontinued from the study.

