11.4.3 Missing Data

The primary analyses using MMRM method will be performed on the ITTOD and ITTFSN population with observed data only. Efficacy analyses may also be conducted using the ITT, ITTOD, and ITTFSN populations with multiple imputation under missing at random (MAR) and missing not at random (MNAR) assumptions. Per-protocol population analysis may also be conducted to assess sensitivity. Further detail will be described in the SAP.

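### Early termination requires only safety assessments, so the dryness and staining scores at exit may go unrecorded, and the missing-data assumption of the primary MMRM becomes harder to support

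*Protocol*

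**What the plan says.** Three places govern subjects who leave early, and all three speak only of safety.

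- Protocol Section 9.3.11: "all safety evaluations that are to be performed at Visit 9 should be performed on the day of discontinuation", or as the investigator sees fit.
- Protocol Section 5: early leavers "will be asked to complete safety assessments prior to commencement of alternative DED therapy", if possible. They are not replaced.
- SAP Section 3.1 repeats the Section 5 text.

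Protocol Section 7.2 defines the safety measures. The list opens with "Visual acuity at distance utilizing an ETDRS chart" and continues with slit lamp, adverse event query, IOP and dilated fundoscopy. The dryness VAS and fluorescein staining are not on it. The VAS is, however, in the procedure list of every scheduled visit from 1 to 9.

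On analysis, Protocol Section 11.4.3 states: "The primary analyses using MMRM method will be performed on the ITTOD and ITTFSN population with observed data only". The same section says that multiple imputation under missing at random (MAR) and missing not at random (MNAR) may also be done, and leaves detail to the SAP. SAP Section 8.2 is blacked out after its opening words. Protocol Section 10.4 adds: "Unmasked subjects will be discontinued from the study".

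**The concern.** An MMRM on observed data gives valid estimates when, given the scores already recorded, leaving does not depend on the unrecorded ones. The score most likely to carry information about leaving is the one on the day the subject leaves. The plan arranges a contact at that point, and asks for it before other dry eye therapy begins, but does not ask for the primary outcome.

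At stake is how well the MAR assumption behind the primary comparison can be defended. If leaving depends on the exit score and that score is missing, the treatment effect can be biased in either direction: toward the null if more vehicle subjects leave because they are doing badly, away from it if more active subjects do. An MNAR analysis can bound this but cannot supply the missing score, and the protocol does not commit to one.

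**Working it through.** **1. The plan's own figures.** Protocol Section 11.3 gives 54 per arm for dryness and 39 for staining, at alpha 0.05 and 90% power. The effect size and SD are not in the readable text, so these cannot be reproduced. Solving backwards (two-sided, normal approximation), d = (1.960 + 1.282) × √(2/n):

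- n = 54: 3.242 × 0.1925 = 0.624 SD
- n = 39: 3.242 × 0.2265 = 0.734 SD

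This sets a scale for the effect; it does not check the sample size. No dropout rate is given anywhere, so all dropout figures below are assumptions.

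**2. Bias when leaving depends on the score.** The first simulation had 400,000 subjects per arm, six visits (Weeks 2 to 12), a true effect of 0.5 SD and exchangeable within-subject correlation of 0.5 or 0.7. The hazard of leaving was multiplied by e for each SD of worse score. Estimation was by maximum likelihood for monotone dropout, standing in for the unstructured MMRM, without the baseline covariate. Bias is a percentage of the true effect; a minus sign means toward the null.

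| What leaving depends on | Dropout vehicle / active | Exit score not recorded | Exit score recorded |
|---|---|---|---|
| Last recorded score (MAR) | 5–19% / 6–12% | at most 0.1% | not needed |
| Exit score | about 10% / 6% | −1.0% to −1.3% | 0.0% |
| Exit score | about 5% / 9% | +1.1% to +1.5% | 0.0% |
| Exit score | about 5% / 12% | +1.9% to +2.8% | 0.0% |
| Exit score | about 19% / 12% | −1.9% to −3.0% | at most 0.1% |

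A second simulation used an effect of 0.63 SD, covariance 0.5 + 0.5 × AR(0.5), 300,000 per arm, vehicle dropout of 11% to 35%, and varying dependence on the exit score. Bias ran from −1% to −9%, and was 0.0% with the exit score recorded.

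**3. What this means for power.** Take d = 0.624 and the extreme −9%, using power = Φ(d√(n/2) − 1.96) and ignoring the precision lost through dropout itself:

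- n = 54: 0.624 × 5.196 = 3.242, power 90%. With bias, 0.91 × 3.242 = 2.950, power Φ(0.99) = 84%.
- n = 100: 0.624 × 7.071 = 4.412, power 99.3%. With bias, 0.91 × 4.412 = 4.015, power Φ(2.05) = 98%.

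About 100 per arm are randomized. The size of the ocular dryness population (ITTOD) is not readable, so the answer lies somewhere between these two cases if that population has at least 54 per arm.

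**4. Benefit lost after leaving is a separate matter.** Suppose a fraction p of active subjects leave at Week 4 at random, lose all benefit, and the target counts that loss. If benefit is absent at m of the six visits, the true mean effect is d(1 − p × m/6). The MMRM still estimates d, so the bias is 1/(1 − p × m/6) − 1.

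- Benefit already gone at exit (m = 5): p = 0.10 gives 1/(1 − 0.0833) − 1 = 9.1%; p = 0.20 gives 20.0%. In simulation, recording the exit score cut these to about 4% and 9%.
- Benefit still present at exit and lost later (m = 4): p = 0.10 gives 7.1%; p = 0.20 gives 15.4%. In simulation these were 7.3% and 15.3%, with no change when the exit score was recorded.

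**The case against.** The strongest reply is that nothing here demonstrates bias. The MMRM uses every visit up to the last one attended and is unbiased under MAR. No dropout rate, reason or pattern is given, and MNAR imputation is foreseen. This stands. It rules out saying that the primary analysis is biased, but the assumption still has to be defended without the most informative score.

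A second reply is that the scores are not necessarily lost. No text forbids efficacy measures at exit, Section 9.4.2 lets the investigator add assessments at an unscheduled visit, and a subject leaving at a scheduled visit may already have completed the VAS. Appendix 1 and SAP Table 2 are not available in usable form, and after Visit 1 fluorescein staining cannot be read in the procedure lists. This also stands: the gap is that the scores are not required, and it falls mainly on those who leave between visits. If Appendix 1 does list efficacy tests at early termination, it conflicts with Sections 5 and 9.3.11 and should be reconciled with them.

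A reader might also infer that stinging will drive dropout on active, since Protocol Section 2 says it "was reported in most subjects treated in the Phase 1 and the allergic conjunctivitis and dry eye disease Phase 2 clinical trials". The same sentence calls it mostly mild or moderate and brief. The Phase 2a dry eye trial described there used other formulations, nothing readable links stinging to stopping, and leaving because of stinging is not leaving because of the dryness score. The documents do not support the inference.

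**Conclusion.** The text as written leaves the exit dryness and staining scores uncollected for subjects who leave between visits, and this makes the MAR assumption of the primary MMRM harder to support. If leaving depends on the exit score, the illustrated bias is about 1% to 9% of the effect: −1% to −9% toward the null, or +1% to +3% away from it. It is about zero when the score is recorded and dropout depends on nothing else unrecorded. These sizes rest on assumed dropout of roughly 5% to 35% per arm and an assumed strength of dependence. Actual size and direction cannot be derived from the documents.

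A reader might put the bias at 9% to 20% from intolerance on active. The documents do not support that. Those figures come entirely from assuming total loss of benefit, under a target that counts it and that no readable section defines. Where benefit is lost only after the exit day, recording the exit score does not help.

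This is a cheap improvement worth making, not a demonstrated flaw in the primary result.

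**What to change.** - In Protocol Sections 5 and 9.3.11 and SAP Section 3.1, require the dryness VAS and fluorescein staining along with the safety evaluations at early termination, where possible before alternative dry eye therapy starts. Make Appendix 1 consistent.
- In the SAP, assign each exit value to a scheduled visit by a pre-specified window rule and include it in the MMRM.
- Make the MNAR sensitivity analysis mandatory and specify it, for example as delta-adjusted or reference-based imputation.
- Keep any value obtained after a subject is unmasked out of the primary analysis, since a self-reported score and a graded stain could both be influenced by knowing the treatment.

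The cost is wording in two documents, a few extra minutes at a contact already planned, and a visit-assignment rule for off-schedule values. The collection step has to be in place before subjects leave, because an exit score cannot be obtained afterwards.
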